# **Description of Subject Population**

#### Sample #1

Specify subject population

US adults health care workers

Number of completers required to accomplish study aims

1200

Projected number of subjects who will be enrolled to obtain required number of completers

1200

Age range of subject population

18-80

Gender, Racial and Ethnic Breakdown

It is expected the sample will roughly mirror the US healthcare workers population:

Anticipated gender distribution: 73% female, 27% male

Anticipated racial distribution: 72% white only, 21% African American only, 5% Asian only, 2% other, 5%

2+ races

Anticipated Hispanic Ethnic Distribution: 10% Hispanic, 90 % Non-Hispanic

Description of subject population

Participants recruited using Amazon Mechanical Turk (AMT) will be adults in the U.S.

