## **Specific Aims and Hypotheses**

Specific Aims and Hypotheses

The overarching goal of this study is to examine the effect of video intervention in reducing stigma and fear, and improving help seeking behavior among health care providers across the US.

In a sizable randomized controlled trial (N=1,200, general population), with pre-, post- and follow-up assessments (day 14, day 30 **and 90 day**), we aim to (1) determine whether video-based intervention reduce stigma and fear, and increase help-seeking behavior in relation to COVID-19 among health care providers, and (2) compare high risk areas (e.g., NY) to low risk areas (e.g., Montana) on intervention outcomes, and (3) test whether symptoms of depression, anxiety, PTSD and Moral Injury, that will be measured by Patient Health Questionnaire (PHQ-9), Generalized Anxiety Disorder (GAD-7), the Primary Care PTSD Screen for DSM-5 (PC-PTSD-5), and the Moral Injury Events Scale (MIES) would change overtime.

Hypotheses: We hypothesize that (1) the brief video intervention will have greater impact in reducing stigma and fear, and in increasing help-seeking behavior in relate to COVID-19 than the control groups in comparison to pre-intervention and to non-video conditions, (2) High risk areas will have increased baseline rates of anxiety, depression and PTSD, and (3) the brief video is expected to have greater impact in reducing symptoms of depression, GAD and PTSD.

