## **Study Procedures**

Describe the procedures required for this study

Participants will be randomly assigned to either a) a 120-second video-based intervention (day 1 and a "booster intervention" of the same content on day 14 of the study) featuring the personal story of a health care provider with COVID-19, his struggles and barriers to care, (b) video-based intervention (day 1 only), and a written description of the same story on day 14 (c) no-intervention control arm (questionnaires only).

Participants of all study arms will be invited to participate in a follow up survey in days 14, 30 and 90. We will invite the participants by using AMT messaging system.

The video content/written vignette: "Martha is a 35-year-old nurse who lives in NYC with her husband (Dave). She works at intensive care unit in a large hospital, and her husband was fired recently from his job as a waiter due to COVID-19. She has never been diagnosed with anxiety, depression or any other mental health issues. Lately, she finds herself experiencing nightmares as well as unexpected fears. She is feeling worried about money, about what might happen if she becomes infected with COVID-19, and about the safety of her parents as well. To Martha it seems that everything has changed since the pandemic began. Recently these worries mean she has had trouble falling asleep, she feels depressed and he feels anxious. Her husband suggested that she could try seeking help. When he first suggested this she dismissed him

saying, "What if people know I went to a psychologist? They might think I'm crazy. Also, what if they suggest I take meds? I don't want to take any... And if my colleges found out they might think I'm weak...". Martha was very resistant to even the idea at first. After a while however, when she realized that how she felt was only getting worse, she agreed to seek professional help. She found a therapist that she now meets with once a week, and since this started, she has reported that she is feeling much better."

You can upload charts or diagrams if any

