#### **Assessment Instruments**

Create a table or give a brief description of the instruments that will be used for assessment Questions for the pre- and post-intervention (day 1) and follow-ups (day 14, day 30 and **day 90**). Baseline Questionnaire (will be conducted pre intervention only) will include four questions regarding demographics (age, sex, ethnicity and race). Based on previous studies it is estimated the response time will be around 30 seconds.

Three questionnaires will be conducted at pre- and post-intervention (day 1) and follow-up (day 14, day 30 and day 90):

- 1. Attitude towards COVID-19 attitude towards COVID-19 questions were adapted from a measure created by Berger et al. about stigma and fear towards people with HIV. The questionnaire will include six questions and based on previous studies it is estimated the response time for 50 seconds.
- 2. Attitude towards seeking help Attitude towards help seeking will be based on the ATSPPH-SF (Attitudes Towards Seeking Professional Psychological Help Scale), and will include 5 questions (0-disagree, 3-agree). One table will be created to include all 5 questions in one screen. Based on previous studies it is estimated the response time will be around 40 seconds.
- 3. COVID-19 related behaviors and experiences was developed by the researchers and will include six questions regarding social media use, news consumption, social contact, previous contact with a known COVID-19 patient and if the participant has been tested for COVID-19. It is estimated the response time will be around 50 seconds.

Three questionnaires will assess clinical symptoms and will be conducted at pre-intervention (day 1) and follow-up (day 14, day 30, and **day 90**):

- 1. GAD-7 questionnaire will include 7 questions that assess anxiety
- 2. PHQ-9 questionnaire will include 9 questions to assess depression
- 3. Primary Care PTSD screen for DSM-5 will include 5 yes/no questions to assess PTSD. Three tables will be created, one for each questionnaire. Based on previous studies it is estimated the response time will be 150 seconds.

One questionnaire will assess Moral Injury (MIES), and includes 9 items (50 seconds).

In sum, the estimate time for day 1 (pre and post intervention) is 7-9 minutes for intervention groups and 5-7 minutes for control. The estimate time for each follow up is 4-7 minutes (days 14, 30 and 90).

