#### Risks/Discomforts/Inconveniences

Risks that could be encountered during the study period

Breach of confidentiality is the main risk of the study. Another potential risk is that participants may experience mild psychological distress when answering questions about COVID-19, due to its sensitive nature.

Describe procedures for minimizing risks

For both of these risks, participants will be reminded that their responses are completely anonymous and that they are free to select "prefer not to answer" if they do not wish to answer a question or end their study participation at any time. Further ways to address the risk of breach of confidentiality are discussed in the Methods to Protect Confidentiality section.

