# **Compensation and/or Reimbursement**

Will compensation or reimbursement for expenses be offered to subjects?

Please describe and indicate total amount and schedule of payment(s).

Include justification for compensation amounts and indicate if there are bonus payments.

Participants will be compensated \$4.40 in total for participating in the study (\$1.10 for day 1, \$1.10 for the follow-up on day 14, \$1.10 for the follow-up on day 30, and \$1.10 for the follow-up on day 90)), a competitive rate on AMT for such a short study. At the conclusion of each part of the study, a "completion code" is displayed to each participant by the Qualtrics software. Participants are instructed to input this code on the AMT web page where they signed up to participate in the study. Once a participant completes the study and inputs the correct code, the researchers will credit \$1.10 to his/her AMT user account on each day of participation (for a possible total of \$4.40). There are no bonus payments associated with this study.

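### The plan gives 1200 both as the completers needed and as the number enrolled to obtain them; on any follow-up reading of completer, the two agree only with zero loss

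*Combined protocol and SAP*

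**What the plan says.** The Sample #1 table has two adjacent entries. Against "Number of completers required to accomplish study aims" it gives 1200. Against "Projected number of subjects who will be enrolled to obtain required number of completers" it also gives 1200. The Lay Summary and the Specific Aims repeat N=1,200. No section defines a completer.

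On follow-up, the documents say the following:

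- Specific Aims and Hypotheses describes a randomised trial "with pre-, post- and follow-up assessments (day 14, day 30" and day 90). Aim 3 concerns change in symptoms over time.
- Assessment Instruments: "Three questionnaires will assess clinical symptoms and will be conducted at pre-intervention (day 1) and follow-up (day 14, day 30, and" day 90). These scales (GAD-7, PHQ-9 and the PTSD screen) are not repeated straight after the intervention.
- The Statistical Analysis Plan models treatment-seeking intentions at four time points up to day 30 and symptoms at three. Its post hoc comparisons include change from baseline to day 30.
- Study Procedures: "Participants of all study arms will be invited to participate in a follow up survey in days 14, 30 and 90". The invitations go through the AMT messaging system.
- Risks/Discomforts/Inconveniences: participants may "end their study participation at any time".
- Compensation and/or Reimbursement pays $1.10 for each of four parts, up to $4.40, with a completion code at the end of each part.

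The documents give no expected loss, over-recruitment, replacement rule, power, effect size or standard deviation.

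**The concern.** The second entry on the form is there to allow for loss: it asks how many must be enrolled so that the required number complete. Giving the same figure twice says that nobody who enrols will fail to complete. That is hard to reconcile with three separately invited online surveys over 90 days, each optional and each paid on its own.

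What is at stake is the meaning of the stated sample size. A reader cannot tell whether 1200 is the number who start, the number who finish day 1, or the number expected at follow-up. If it is a follow-up number, the design as written does not deliver it unless retention is complete. If it is a day-1 number, it is larger than the sample on which aim 3 will rest.

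**Working it through.** **Inputs from the documents.** Completers required C = 1200 and projected enrolment E = 1200 (Sample #1); three arms and two-sided 0.05 (Statistical Analysis Plan); follow-up at days 14, 30 and 90 (Study Procedures).

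**Inputs not in the documents, assumed here.** Response at one follow-up wave r = 95%, 90% or 80%; equal allocation; 80% power.

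**Step 1. The plan's own figure.** With proportion lost d, E = C/(1 − d). Setting 1200 = 1200/(1 − d) gives d = 0 as the only solution. The stated enrolment is reproduced only with zero loss.

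**Step 2. Which wave do the aims need?** Setting the sections side by side:

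- Aim 3: the three symptom scales are taken once on day 1, before the intervention. One measurement gives no change, so follow-up is needed.
- The two video arms differ only on day 14 (repeat video or written story). Any effect of that difference can appear only at day 14 or later.
- The item on actual contact with mental health care is asked only at day 90.
- The SAP's overall change runs from baseline to day 30.
- Two elements need day 1 only: the hypothesis that "High risk areas will have increased baseline rates of anxiety, depression and PTSD", and the pre-to-post part of hypothesis 1.

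The aims as a whole therefore cannot be met from day-1 data.

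**Step 3. What 1200 enrolled leaves.** Responders at one wave = 1200 × r. For illustration, detectable difference = (z₀.₉₇₅ + z₀.₈₀) × √(2/n) = 2.8016 × √(2/n) SD, where n = responders/3. This is an unadjusted comparison of two arms at one time point, not the planned group × time test. The relative increase is 1/√r − 1.

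| Assumed r | Responders | Below 1200 | n per arm | Detectable difference | Increase |
|---|---|---|---|---|---|
| 100% | 1,200 | 0 | 400 | 0.198 SD | – |
| 95% | 1,140 | 60 | 380 | 0.203 SD | 2.6% |
| 90% | 1,080 | 120 | 360 | 0.209 SD | 5.4% |
| 80% | 960 | 240 | 320 | 0.221 SD | 11.8% |

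**Step 4. Loss over several waves.** The table concerns a single wave. If the same proportion were lost at each of the three follow-ups (again an assumption), 1200 × 0.95³ = 1,029, 1200 × 0.90³ = 875 and 1200 × 0.80³ = 614 would remain by day 90, a cumulative loss of 14.3%, 27.1% and 48.8%.

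**The case against.** The best defence is that a completer is someone who finishes day 1. The compensation section supports this to a degree: it issues a code at the end of each part, and the sentence that begins "Once a participant completes the study and inputs the correct code" ends in a $1.10 credit for one day of participation, so completing can mean completing one part. Day-1 completers are also the people invited back, and aim 3 could be tested in those who return. On this reading 1200 and 1200 need no follow-up retention. This stands as a possible reading, and because of it the entry is not proved to be a failed sum on every meaning. But it fits the field poorly, because the field asks for the number needed for the study aims and day-1 data do not meet them. It also leaves the number behind aim 3 unstated.

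It is also fair to say that the documents show loss to be possible but give no rate, and that every retention figure above is assumed. That stands too. The identity in Step 1 depends on none of those figures; only the size does.

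A further objection is to the remedy: the form asks for a required number, and replacing it with a smaller expected number would lower the requirement to suit the enrolment. That is right, and the change proposed below keeps the two apart.

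A reader might go further and infer that the trial is underpowered. The documents do not support this: they state no power, effect size or standard deviation, so there is no target for attrition to breach. Nor do they show that the analysis drops people with missing waves. The SAP describes a repeated-measures model and does not limit it to completers. Who enters that model is a separate matter of missing detail.

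**Conclusion.** The point holds in a limited form. On any follow-up reading, enrolling 1200 delivers 1200 completers only with zero loss, and the plan makes no provision for loss. Only a day-1 reading removes the conflict, and then 1200 overstates the sample for aim 3. Either way, the stated size needs to be restated.

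The size cannot be fixed from the documents. Under assumed one-wave response of 95% to 80%, follow-up falls 60 to 240 short of the stated completer figure. The cost in precision is small at 95% and modest at 80%. Those precision figures also assume equal arms, 80% power and a simple two-arm comparison.

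It would be tempting to conclude that more people must be enrolled, for example 1200/0.90 = 1,334 under 10% loss. That does not follow, because no calculation shows that 1200 at follow-up is needed. The defect is in what the number is said to be.

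**What to change.** Without enrolling more:

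1. Label 1200 as the number enrolled and randomised on day 1, and stop presenting it as the number completing follow-up.
2. Say which wave completer refers to wherever the word is used.
3. State separately the smaller number expected at day 30 (the last time point in the SAP) and at day 90, under a stated retention assumption with its basis, and give the precision those numbers provide.
4. Do not call the expected numbers required unless a sample-size basis is supplied.

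The cost is a change of wording in the two Sample #1 entries and a short statement of expected numbers and precision. Enrolment, procedures and payments are unchanged. The sponsor has to commit to a definition and a retention assumption. The drawback is that the stated completer figure becomes less favourable than 1200.

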#### **Recruitment Procedures**

Describe settings where recruitment will occur

Participants will be recruited via Amazon Mechanical Turk (AMT: https://www.mturk.com/mturk/). AMT is a website that allows interested people across the US to respond to tasks, including completion of surveys, for a small amounts of compensation. AMT requires users to be over 18 years old. For this study the age range will be defined as 18-80. No demographic restrictions will be placed on participants, other than being health care workers and a resident in the U.S.

How and by whom will subjects be approached and/or recruited?

A posting (the Information Sheet attached to this protocol) will be listed on AMT once the study is approved by IRB. Participants can peruse the tasks available via AMT and read the information posted if they desire. The posting will explain the terms and conditions of the study. If participants agree to the conditions and consent to participate, they will click on a link that will direct them to complete the study procedures via Qualtrics.com (a secured, online data-collection platform that will store the study data in a password protected

account); if they do not consent to the conditions, they will not participate.

How will the study be advertised/publicized?

As stated above, a posting (the Information Sheet attached to this protocol) will be listed on AMT once the study is approved by the IRB. In answering "yes" to the question below about whether we have recruitment material requiring review, we are referring to the Information Sheet.

Do you have ads/recruitment material requiring review at this time?

Yes

Does this study involve a clinical trial?

No

#### **Concurrent Research Studies**

Will subjects in this study participate in or be recruited from other studies? No

#### Inclusion/Exclusion Criteria

Name the subject group/sub sample

AMT participants

Create or insert table to describe the inclusion criteria and methods to ascertain them

Study Criteria Methods of Ascertainment

Healthcare AMT setting will be used to limit responders to of

workers healthcare workers only

80>Age>18 AMT requires responders to be at least 18 years old and

lower than 80

[name]

English AMT settings will be used to limit responders to English

speakers speakers only

US residents AMT settings will be used to limit responses to users in

US only

Create or insert table to describe the exclusion criteria and methods to ascertain them

Study Criteria Methods of Ascertainment

Age<18 AMT requires responders to be at least 18 years old

Age>80 AMT settings will be used to limit the age to 80 years old Non healthcare AMT settings will be used to ensure that only healthcare

workers will participate

Non English AMT settings will used to ensure that only English

speakers speakers will participate.

### **Waiver of Consent/Authorization**

Indicate if you are requesting any of the following consent waivers

Waiver of consent for use of records that include protected health information (a HIPAA waiver of Authorization)

No

Waiver or alteration of consent

Nο

Waiver of documentation of consent

Yes

Waiver of parental consent

No

#### **Consent Procedures**

Is eligibility screening for this study conducted under a different IRB protocol?

No

Describe procedures used to obtain consent during the screening process

n/a

**Describe Study Consent Procedures** 

As stated earlier, a posting (the Information Sheet attached to this protocol) will be posted on AMT once the study is approved by the IRB. Participants can peruse the tasks available via AMT and read the information posted if they desire. The posting will explain the terms and conditions of the study. If participants agree to the conditions and consent to participate, they will click on a link that will direct them to complete the study

procedures via Qualtrics.com (a secure, online data-collection platform that will store the study data in a password-protected account); if they do not consent to the conditions, they will not participate.

Indicate which of the following are employed as a part of screening or main study consent procedures

Information Sheet

### **Waiver of Documentation of Consent**

Would the consent form signature be the only link between the subject's identity and the research data? Yes

Is breach of confidentiality the main study risk?

Yes

Describe the study component(s) for which waiver of documentation is requested The information sheet will act as consent, but no signature will be obtained because the information sheet will be presented onscreen to participants recruited via the internet.

## Persons designated to discuss and document consent

Select the names of persons designated to obtain consent/assent Type in the name(s) not found in the above list n/a

## **Study Procedures**

Describe the procedures required for this study

Participants will be randomly assigned to either a) a 120-second video-based intervention (day 1 and a "booster intervention" of the same content on day 14 of the study) featuring the personal story of a health care provider with COVID-19, his struggles and barriers to care, (b) video-based intervention (day 1 only), and a written description of the same story on day 14 (c) no-intervention control arm (questionnaires only).

Participants of all study arms will be invited to participate in a follow up survey in days 14, 30 and 90. We will invite the participants by using AMT messaging system.

The video content/written vignette: "Martha is a 35-year-old nurse who lives in NYC with her husband (Dave). She works at intensive care unit in a large hospital, and her husband was fired recently from his job as a waiter due to COVID-19. She has never been diagnosed with anxiety, depression or any other mental health issues. Lately, she finds herself experiencing nightmares as well as unexpected fears. She is feeling worried about money, about what might happen if she becomes infected with COVID-19, and about the safety of her parents as well. To Martha it seems that everything has changed since the pandemic began. Recently these worries mean she has had trouble falling asleep, she feels depressed and he feels anxious. Her husband suggested that she could try seeking help. When he first suggested this she dismissed him

saying, "What if people know I went to a psychologist? They might think I'm crazy. Also, what if they suggest I take meds? I don't want to take any... And if my colleges found out they might think I'm weak...". Martha was very resistant to even the idea at first. After a while however, when she realized that how she felt was only getting worse, she agreed to seek professional help. She found a therapist that she now meets with once a week, and since this started, she has reported that she is feeling much better."

You can upload charts or diagrams if any

#### **Assessment Instruments**

Create a table or give a brief description of the instruments that will be used for assessment Questions for the pre- and post-intervention (day 1) and follow-ups (day 14, day 30 and **day 90**). Baseline Questionnaire (will be conducted pre intervention only) will include four questions regarding demographics (age, sex, ethnicity and race). Based on previous studies it is estimated the response time will be around 30 seconds.

Three questionnaires will be conducted at pre- and post-intervention (day 1) and follow-up (day 14, day 30 and day 90):

- 1. Attitude towards COVID-19 attitude towards COVID-19 questions were adapted from a measure created by Berger et al. about stigma and fear towards people with HIV. The questionnaire will include six questions and based on previous studies it is estimated the response time for 50 seconds.
- 2. Attitude towards seeking help Attitude towards help seeking will be based on the ATSPPH-SF (Attitudes Towards Seeking Professional Psychological Help Scale), and will include 5 questions (0-disagree, 3-agree). One table will be created to include all 5 questions in one screen. Based on previous studies it is estimated the response time will be around 40 seconds.
- 3. COVID-19 related behaviors and experiences was developed by the researchers and will include six questions regarding social media use, news consumption, social contact, previous contact with a known COVID-19 patient and if the participant has been tested for COVID-19. It is estimated the response time will be around 50 seconds.

Three questionnaires will assess clinical symptoms and will be conducted at pre-intervention (day 1) and follow-up (day 14, day 30, and **day 90**):

- 1. GAD-7 questionnaire will include 7 questions that assess anxiety
- 2. PHQ-9 questionnaire will include 9 questions to assess depression
- 3. Primary Care PTSD screen for DSM-5 will include 5 yes/no questions to assess PTSD. Three tables will be created, one for each questionnaire. Based on previous studies it is estimated the response time will be 150 seconds.

One questionnaire will assess Moral Injury (MIES), and includes 9 items (50 seconds).

In sum, the estimate time for day 1 (pre and post intervention) is 7-9 minutes for intervention groups and 5-7 minutes for control. The estimate time for each follow up is 4-7 minutes (days 14, 30 and 90).

